### **4.3. Selection of Study Population**

The study population will include approximately 800 premenopausal women aged 18 to 51 years with endometriosis-associated pain.

Deviations from inclusion and exclusion criteria are not allowed because they can potentially jeopardize the scientific integrity of the study, regulatory acceptability, or patient safety. Therefore, adherence to the criteria as specified in the protocol is essential. Any questions regarding patient eligibility and entry criteria should be discussed with the medical monitor.

#### **4.3.1. Inclusion/Exclusion Criteria**

Inclusion Criteria (all inclusion criteria must have been met prior to randomization):

1. Completed 24 weeks of study drug treatment and study participation in either MVT-601-3101 or MVT-601-3102;
2. Has voluntarily signed and dated the informed consent form prior to initiation of any study-specific procedures for MVT-601-3103;

Note: Procedures conducted as part of the parent study that also serve as baseline procedures for this study will be done under the informed consent for the parent study.

3. Is not expected to undergo gynecological surgery or other surgical procedures for treatment of endometriosis (including ablation, shaving, or excision) during the study, including during the Follow-Up Period, and the patient does not desire such treatment during this time frame;
4. Has a negative urine pregnancy test at the Week 24/Baseline visit;
5. Has agreed to continue to use only study-specified analgesic medications during the study and is not known to be intolerant to these;
6. Agrees to continue to use acceptable non-hormonal contraceptive methods as described in Section 4.6 consistently during the Open-Label Treatment Period and for at least 30 days after the last dose of study drug. However, the patient is not required to use the specified non-hormonal contraceptive methods if she:
  - a. Has a sexual partner(s) who was vasectomized at least 6 months prior to the Week 24/Baseline visit;
  - b. Had a bilateral tubal occlusion (including ligation and blockage methods such as Essure™), at least 6 months prior to the Week 24/Baseline visit (patients with Essure must have prior confirmation of tubal occlusion by hysterosalpingogram) and there must be no evidence of post-Essure syndrome;
  - c. Has a non-hormonal intrauterine device (eg, Paragard®) placed in the uterus;
  - d. Is not sexually active with men; periodic sexual relationship(s) with men requires the use of non-hormonal contraception as noted above;
  - e. Practices total abstinence from sexual intercourse, as her preferred lifestyle; periodic abstinence is not acceptable.

#### Exclusion Criteria

1. Has had a surgical procedure for treatment of endometriosis at any time during the parent study (MVT-601-3101 or MVT-601-3102);
2. Has any chronic pain or frequently recurring pain condition, other than endometriosis, that is treated with opioids or requires analgesics for  $\geq 7$  days per month;
3. Has a weight that exceeds the weight limit of the DXA scanner or has a condition that precludes an adequate DXA measurement at the lumbar spine and proximal femur (eg, bilateral hip replacement, spinal hardware in the lumbar spine);
4. Has a Z-score  $< -2.0$  or has a  $\geq 7\%$  decrease in bone mineral density from the parent study Baseline at lumbar spine, total hip, or femoral neck based on the parent study Week 24 DXA assessment of bone mineral density;
5. Anticipated to use any prohibited medications as detailed in Section 5.10.1;

6. Has any contraindication to treatment with low-dose estradiol and norethindrone acetate, including:
  - a. Known, suspected, or history of breast cancer;
  - b. Known or suspected estrogen-dependent neoplasia;
  - c. Active deep vein thrombosis or pulmonary embolism, or history of these conditions prior to the Week 24/Baseline visit;
  - d. History of or active arterial thromboembolic disease, including stroke and myocardial infarction;
  - e. Known anaphylactic reaction or angioedema or hypersensitivity to estradiol or norethindrone acetate;
  - f. Known protein C, protein S, or antithrombin deficiency, or other known thrombophilia disorders, including Factor V Leiden;
  - g. Migraine with aura;
  - h. History of porphyria;
7. Has current active liver disease from any cause;
8. Has a systemic autoimmune disease (eg, systemic lupus erythematosus, Sjogren's syndrome, rheumatoid arthritis, polymyositis, systemic sclerosis, psoriasis, psoriatic arthritis, vasculitic syndromes, etc); psoriasis not requiring or anticipated to require systemic therapy is permitted;
9. Had any of the following clinical laboratory abnormalities at the parent study Week 20 visit or, if available, any subsequent visit in one of the parent studies (MVT-601-3101 or MVT-601-3102):
  - a. Alanine aminotransferase (ALT) or aspartate aminotransferase (AST) > 2.0 times the upper limit of normal (ULN); or
  - b. Bilirubin (total bilirubin) > 1.5 x ULN (or > 2.0 x ULN if secondary to Gilbert syndrome or pattern consistent with Gilbert syndrome);
10. Is currently pregnant or lactating, or intends to become pregnant during the study period or within 1 month after the last dose of study drug, or plans to donate ova during the study period or within 2 months after the last dose of study drug;
11. Has a decline in presenting visual acuity score, as defined below (unless explained by refractive error or approved by the sponsor):
  - a. 90 or lower and 5 or more points lower at Week 24/Baseline visit relative to the parent study Baseline visit; or
  - b. The presenting visual acuity score has decreased by ten or more points at the Week 24/Baseline visit relative to the parent study Baseline visit;

Note: Visual acuity score must have been obtained with corrective lenses, if applicable.

12. Is inappropriate for participation in this study because of conditions that may interfere with interpretation of study results or prevent the patient from complying with study requirements, as determined by the investigator, sub-investigator, or medical monitor;
13. Met a withdrawal criterion in the parent study (MVT-601-3101 or MVT-601-3102).

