#### **4.5. Removal of Patients from Therapy**

Completion of the Week 104 visit defines completion of the study. Patients may withdraw consent to participate in the study and discontinue treatment at any time for any reason. Investigators or the medical monitor may remove patients from therapy under this protocol for reasons of safety and/or lack of compliance as discussed below. Patients removed from therapy for any reason will undergo the assessments for the Early Termination visit (see the Week 104 visit on the Schedule of Activities, Section 1.1) and will have a Follow-up visit to assess safety approximately 30 days after the end of study drug treatment (ie, after the patient's last dose of study medication). When patients complete the study or early terminate from the study, they must be deactivated from the study in the interactive voice response system/interactive web response system (IVRS/IWRS), eDiary, and tablet device.

The following safety and/or compliance events will result in the removal of patients from therapy either permanently or until the etiology of the problem has been identified and resolved:

- Any adverse event that is intolerable to the patient and that cannot be ameliorated by the use of adequate medical intervention, or that in the opinion of the investigator or medical monitor would lead to undue risk to the patient if dosing continued;
- If it is discovered after enrollment that a patient failed to meet protocol entry criteria and continued participation poses an unacceptable risk to the patient's health;
- If the following liver test abnormalities develop, study drug should be discontinued immediately with appropriate clinical follow-up (including repeat laboratory tests, until a patient's laboratory profile has returned to normal/baseline status):
  - ALT or AST > 8 x ULN; or
  - ALT or AST > 5 x ULN and persists for more than 2 weeks; or
  - ALT or AST > 3 x ULN in conjunction with elevated total bilirubin > 2 x ULN or international normalized ratio (INR) > 1.5; or
  - ALT or AST > 3 x ULN with appearance of fatigue, nausea, vomiting, right upper quadrant pain or tenderness, fever, rash and/or eosinophilia (> 5%);

- 
- QT interval by the Fridericia correction (QTcF) prolongation of more than 500 msec read by a cardiologist;
  - Evidence of endometrial hyperplasia or endometrial carcinoma on endometrial biopsy;

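### Four conditions that bar entry as contraindications to the add-back have no named stopping rule and no bar on restart when they first arise on treatment

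*Protocol*

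**What the plan says.** Exclusion Criterion 6 (Protocol Section 4.3.1, repeated in the synopsis) applies to a woman who "Has any contraindication to treatment with low-dose estradiol and norethindrone acetate, including" eight listed items, 6a to 6h. Four matter here:

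- 6c: "Active deep vein thrombosis or pulmonary embolism, or history of these conditions prior to the Week 24/Baseline visit"
- 6d: "History of or active arterial thromboembolic disease, including stroke and myocardial infarction"
- 6e: "Known anaphylactic reaction or angioedema or hypersensitivity to estradiol or norethindrone acetate"
- 6g: "Migraine with aura"

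Section 5.1 gives the add-back to every patient for 80 weeks.

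Section 4.5 sets out the events that take a patient off therapy. Its lead-in says that they lead to "removal of patients from therapy either permanently or until the etiology of the problem has been identified and resolved". The first bullet covers an adverse event that the patient cannot tolerate and that treatment cannot relieve, or one "that in the opinion of the investigator or medical monitor would lead to undue risk to the patient if dosing continued". The second begins "If it is discovered after enrollment that a patient failed to meet protocol entry criteria" and also requires that continuing would be unacceptably risky.

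Section 5.5 deals with toxicity of grade 3 or above that medical treatment cannot relieve. Dosing is interrupted until the toxicity falls to grade 2 or below, and may then resume if the sponsor or its designee approves in writing.

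**The concern.** The entry rule and the continuation rule do not match. At entry, even a resolved thrombosis or a past arterial event is enough to keep a woman off the drug. On treatment, the same diagnosis triggers no specific action, and a woman removed for it may be eligible to resume. A history that forbids starting therefore does not forbid restarting.

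What is at stake is patient safety. The four conditions are ones the protocol itself calls contraindications to a component that everyone takes. With about 320 sites planned, a rule that depends on individual opinion can be applied differently to the same event. No sample size, power or error rate is affected.

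**Working it through.** No design formula applies, so the check compares the entry list with the stopping list in the current protocol text.

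**Step 1: the nine removal bullets in Section 4.5.** They are (1) intolerable or undue-risk adverse event; (2) entry failure found later; (3) liver test thresholds; (4) QTcF above 500 msec; (5) endometrial hyperplasia or carcinoma; (6) bone density loss of 7% or more; (7) gross noncompliance; (8) pregnancy; (9) malignant breast finding.

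**Step 2: match the eight items of Exclusion 6 to those bullets.**

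- 6a breast cancer: on-treatment form named in bullet 9.
- 6b estrogen-dependent neoplasia: partly named, in bullets 5 and 9.
- 6c venous thromboembolism: not named.
- 6d arterial thromboembolism: not named.
- 6e allergy to the add-back hormones: not named.
- 6g migraine with aura: not named.
- 6f thrombophilia and 6h porphyria: not named, but relevant only if first diagnosed on treatment, so not counted.

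Tally: 2 items fully or partly named + 4 that can newly arise and are not named + 2 not counted = 8. Bullets naming any of the four: 0 of 9.

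**Step 3: can the general bullets reach the four?** Bullet 2 cannot, because a woman who was eligible at entry and has a thrombosis later did not fail the entry criteria. Bullet 1 can, by two routes. An event that is intolerable and cannot be relieved must lead to removal. An event that is tolerable or treatable leads to removal only if the investigator or medical monitor forms the undue-risk opinion; once formed, removal is mandatory. A treated deep vein thrombosis and a tolerable new migraine with aura fall on the second route.

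**Step 4: return to treatment.** The lead-in permits temporary removal for any listed event and excepts none of the four. Section 5.5 applies only where its grade 3 trigger is met; there too, restart with sponsor approval has no exception for them.

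**Step 5: other visible text.** The prohibited-medication table in Section 5.10.1 does not list anticoagulants, and it expressly allows clopidogrel and aspirin up to 325 mg per day. Treating a thrombosis would not by itself stop study drug under the listed classes, although the table is said not to be exhaustive.

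**Step 6: size.** The exposure ceiling is 800 women × 80 weeks × 7 / 365.25 = 1,226.6 patient-years, assuming no dropout. The document gives no event rate for the four conditions, and no proportion of such events in which dosing would continue, so the ceiling cannot be turned into a count of women affected.

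**The case against.** The best defence is that nothing is contradicted. Exclusion 6 governs entry, and no sentence tells a site to keep dosing a woman with a new thrombosis. The undue-risk limb is mandatory once either the investigator or the medical monitor holds that opinion, and the same protocol tells both of them that these conditions contraindicate the add-back. Most of the named bullets (liver tests, QTcF, biopsy, bone density, pregnancy, breast imaging) respond to scheduled tests that can be positive without symptoms. Thrombosis, stroke, anaphylaxis and migraine present clinically, which is what bullet 1 is for. Return is also gated: temporary removal lasts until the cause is found and resolved, bullet 1 applies again on resumption, and a Section 5.5 restart needs written sponsor approval.

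Much of this stands. Major events would probably be caught, so a reader who infers that the protocol offers no protection, or gives a right to restart, goes beyond the text. It does not close the gap for treatable or tolerable events, where the outcome turns on opinion. Nor does resolution of the event answer 6c and 6d, under which the history alone is disqualifying at entry.

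The defence also notes that the most relevant text may be unseen. The current version is available only to the start of Section 6.5.2.6. Its contents list shows criteria for withholding or stopping drug only under the liver headings 7.5.1 and 7.5.2, but headings are weak evidence. The preceding version's Table 7-2 row on add-back risk lists monitoring and adverse event recording with no withdrawal rule for these events; it predates later safety additions and cannot stand for the current row. This limit is real.

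**Conclusion.** The point holds as a gap in the stopping rules of Sections 4.5 and 5.5. For four conditions that the protocol treats as contraindications at entry, on-treatment protection is partial and discretionary, and nothing in these sections specifically bars return. It is worth fixing because it concerns patient safety and costs little; it does not undermine the analysis.

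A reader might apply an assumed combined rate of 1 to 10 per 1,000 patient-years to the exposure ceiling and conclude that about 1 to 12 women would be harmed or left on drug (1,226.6 × 0.001 = 1.2; 1,226.6 × 0.010 = 12.3). The document does not support that. The rate is not in it, the ceiling ignores dropout, and the product counts every woman with such an event, not those who would stay on or return to treatment because of the gap. That smaller number is unknown.

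The conclusion rests on the visible current text of Sections 4.3.1, 4.5 and 5.5, and assumes that the current Section 7, including Table 7-2, does not already supply the missing rule.

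**What to change.** Add a bullet to Section 4.5 requiring permanent discontinuation of study drug for any of the following arising on treatment: deep vein thrombosis or pulmonary embolism; stroke, myocardial infarction or other arterial thromboembolism; new migraine with aura; and anaphylaxis, angioedema or confirmed hypersensitivity to either add-back hormone. Keep the last item to estradiol and norethindrone acetate, as 6e does. Extending it to any reaction to study drug would take in relugolix and go beyond the stated contraindication.

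State that the temporary-removal option in the Section 4.5 lead-in and the restart provision in Section 5.5 do not apply to these events. Align Table 7-2 if it does not already say so.

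The cost is one bullet, one sentence and possibly a few more discontinuations. No procedure, visit or analysis has to change.

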#### **4.4. Method of Assigning Patients to Treatment Group and Patient Identification Number**

Eligible patients who sign consent will be identified with the same Patient Identification (ID) Number assigned to the patient during the parent study. This extension study is a single-arm, open-label study, and thus all eligible patients are assigned to the same treatment group of relugolix 40 mg co-administered with low-dose of estradiol and norethindrone acetate (see Section 5.1 for treatment details).

#### **4.5. Removal of Patients from Therapy**

Completion of the Week 104 visit defines completion of the study. Patients may withdraw consent to participate in the study and discontinue treatment at any time for any reason. Investigators or the medical monitor may remove patients from therapy under this protocol for reasons of safety and/or lack of compliance as discussed below. Patients removed from therapy for any reason will undergo the assessments for the Early Termination visit (see the Week 104 visit on the Schedule of Activities, Section 1.1) and will have a Follow-up visit to assess safety approximately 30 days after the end of study drug treatment (ie, after the patient's last dose of study medication). When patients complete the study or early terminate from the study, they must be deactivated from the study in the interactive voice response system/interactive web response system (IVRS/IWRS), eDiary, and tablet device.

The following safety and/or compliance events will result in the removal of patients from therapy either permanently or until the etiology of the problem has been identified and resolved:

- Any adverse event that is intolerable to the patient and that cannot be ameliorated by the use of adequate medical intervention, or that in the opinion of the investigator or medical monitor would lead to undue risk to the patient if dosing continued;
- If it is discovered after enrollment that a patient failed to meet protocol entry criteria and continued participation poses an unacceptable risk to the patient's health;
- If the following liver test abnormalities develop, study drug should be discontinued immediately with appropriate clinical follow-up (including repeat laboratory tests, until a patient's laboratory profile has returned to normal/baseline status):
  - ALT or AST > 8 x ULN; or
  - ALT or AST > 5 x ULN and persists for more than 2 weeks; or
  - ALT or AST > 3 x ULN in conjunction with elevated total bilirubin > 2 x ULN or international normalized ratio (INR) > 1.5; or
  - ALT or AST > 3 x ULN with appearance of fatigue, nausea, vomiting, right upper quadrant pain or tenderness, fever, rash and/or eosinophilia (> 5%);

- 
- QT interval by the Fridericia correction (QTcF) prolongation of more than 500 msec read by a cardiologist;
  - Evidence of endometrial hyperplasia or endometrial carcinoma on endometrial biopsy;
  - If the patient has a  $\geq 7\%$  loss of bone mineral density at lumbar spine, total hip, or femoral neck compared with the parent study Baseline;
  - If the patient, in the opinion of the investigator or the medical monitor, is grossly noncompliant with the protocol's requirements. Gross noncompliance includes  $< 75\%$  compliance with the study drug over  $> 2$  consecutive months; missing multiple study visits; and persistent ( $> 2$  consecutive months) noncompliance ( $< 50\%$  of the required number of days) with eDiary completion up to Week 52 or persistent ( $\geq 2$  eDiary collection cycles) noncompliance ( $< 50\%$  of the required number of days) with eDiary completion from Week 52 to Week 104. Investigators will follow up with the patient and encourage compliance with study drug or eDiary prior to discontinuing her from the study;
  - If the patient becomes pregnant at any time after providing a signed informed consent form, the patient must be withdrawn immediately (see Section 7.8 for information on pregnancy reporting);
  - Evidence of malignant breast lesion(s) or breast carcinoma on Week 52 or Week 104/Early Termination or most recent mammogram or additional breast imaging (see Section 6.5.2.9 for more information on mammogram at Week 52 or Week 104/Early Termination);

Should a patient fail to attend the clinic for a required study visit within the protocol-defined window, the site should attempt to contact the patient and reschedule the missed visit as soon as possible. The site should also counsel the patient on the importance of maintaining the assigned visit schedule and determine whether the patient can and/or should continue in the study based on previous noncompliance. In cases where the patient does not return for the rescheduled visit or cannot be reached to reschedule the missed visit, the site should make every effort to regain contact with the patient. The site should attempt at least three documented telephone calls and if necessary, a certified letter to the patient's last known mailing address so that they can appropriately be withdrawn from the study with a primary reason of "Lost to Follow-up."

#### **4.6. Contraception/Pregnancy Avoidance**

All patients should be counseled at every visit to adhere to the use of protocol allowed contraceptive methods. In this study, medications and devices containing hormones for contraception are excluded, and patients must agree to use non-hormonal contraception throughout the study including through 30 days following the last dose of study drug, unless any of the following apply:

- Has a sexual partner(s) who was vasectomized at least 6 months prior to the Week 24/Baseline visit;
- Had a bilateral tubal occlusion (including ligation and blockage methods such as Essure) at least 6 months prior to the Week 24/Baseline visit (patients with Essure must have prior confirmation of tubal occlusion by hysterosalpingogram) and there must be no evidence of post-Essure syndrome;

- Has a non-hormonal intrauterine device (eg, Paragard) placed in the uterus;
- Is not sexually active with men; periodic sexual relationship(s) with men requires the use of non-hormonal contraception as described below;
- Practices total abstinence from sexual intercourse, as her preferred lifestyle; periodic abstinence is not acceptable.

The only acceptable methods of contraception for those for whom one of the above methods do not apply are:

- Condom (male or female condom) with or without spermicide (cream, spray, foam, gel, suppository, or polymer film);
- Diaphragm with spermicide (condom may or may not be used);
- Cervical cap with spermicide (condom may or may not be used); or
- Vaginal sponge impregnated with spermicide used with a condom.

Patients will be provided with information on acceptable methods of contraception as part of the informed consent process and will confirm with signing of the consent form that they understand the requirements for avoidance of pregnancy during the course of the study. Patients may not donate ova during the course of the study and for 2 months following the last dose of study drug.

A patient may start hormonal contraception 4 weeks after her last study dose of study drug provided her menstrual cycle has returned.

Urine pregnancy tests will be performed according to the Schedule of Activities ([Table 1-1](#); including just prior to receiving the first dose of study drug), and patients will receive continued guidance with respect to the avoidance of pregnancy as part of the study procedures. Patients who become pregnant during the study will be withdrawn from the study and followed for pregnancy outcome (see Section [7.8](#)).

